10.4. Study populations to be evaluated

10.4.1. Total Treated Population (TTP)

The Total Treated Population will include all the enrolled patients that have received at least one dose of the study product (recMAGE-A3 + AS15 ASCI +/- poly IC:LC).

The total treated population will be used for the analysis of clinical activity.

10.4.2. Total Treated Population (TTP) for analysis of efficacy

The intent-to-treat approach will define the Total Treated Population to be used for data analysis of this trial. That means all evaluable patients (i.e. those meeting the eligibility criteria) enrolled in this trial who have received at least one dose of the study treatment, i.e., recMAGE-A3 + AS15 ASCI with or without Poly IC:LC, will be included in the final data analyses. Patients who are lost to follow-up or drop out of study prior to their scheduled evaluation time due to any reason will be treated as non-responders for response determination and censored for time-to-event type of endpoints at the time of their last assessment/follow-up if no relevant event has occurred by then. By-arm analysis will be presented as the main analysis.

10.4.3. According to Protocol (ATP) population for analysis of clinical activity and immunogenicity

A secondary analysis that includes only all eligible patients may be conducted in addition to the primary analysis described above at the discretion of the trial PI and study biostatistician. Other subanalyses may also be considered on the basis of a subset of patients, excluding those for whom major protocol deviations have been identified (e.g., early discontinuation of treatment, major protocol violations, etc.). However, these subanalyses may not serve as the basis for drawing conclusions concerning treatment efficacy, and the reasons for excluding patients from the analysis should be clearly reported. Missing data will not be imputed. A p-value of <0.05 will be considered significant. No multiplicity adjustment will be made in this study.

10.5. Elimination criteria for analysis

As defined in Section 5.8.2, certain medications are prohibited during this study. Among those medications, the following will not require withdrawal of the patient from the study but may determine the patient's evaluability in the according-to-protocol (ATP) analysis.

- Chronic administration of immunosuppressants or other immune-modifying drugs during the study period. The use of prednisone, or equivalent, < 0.125 mg/kg/day (absolute maximum 10 mg/day), inhaled corticosteroids or topical steroids is permitted.
- Administration of a vaccine not foreseen by the study protocol during the prohibited time period as specified in Section 5.8.3.
- Repetitive administration of immunoglobulins and/or any blood products during the study period.

Patients to be excluded from the ATP populations will be identified during a review of data.

10.6. Derived and transformed data

10.6.1. Group definition

The patients will be analyzed according to the treatment group assigned by randomization.

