10. STATISTICAL CONSIDERATIONS

10.1. Primary endpoints

Safety and Toxicity of the two regimens: adverse events and serious adverse events.

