The descriptions and grading scales found in the CTEP Active Version of the NCI Common Terminology Criteria for Adverse Events (CTCAE v.4) will be utilized for AE reporting. The CTEP Active Version of the CTCAE is identified and located on the CTEP website at: http://ctep.cancer.gov/protocolDevelopment/electronic_applications/ctc.htm. All appropriate treatment areas should have access to a copy of the CTEP Active Version of CTCAE. Toxicity data will be summarized using the usual toxicity table by category and worst grade for the two ASCI regimens.

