10.6.3. Safety

For the analysis of adverse events, such as serious adverse events or adverse events by primary MedDRA term, all patients treated will be considered. Patients who did not report an event will be considered as patients without the event.

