10.7.5. Analysis of safety

The safety analyses will be based on the Total Treated population.

The duration of treatment and total number of doses of investigational product administered will be summarized by treatment group.

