10.7.5.1. Adverse events

Adverse events (AEs), including abnormal laboratory values, will be graded according to the CTCAE, Version 4.0 and coded to the preferred term (PT) level using the MedDRA dictionary.

The percentage of patients with adverse event(s) within 30 days of each recMAGE-A3 + AS15 ASCI dose +/- Poly IC:LC will be reported by treatment group with exact 95% confidence intervals, as per MedDRA terminology, by Preferred Term (PT) and System Organ Class (SOC), if appropriate. The same tabulation will be presented for grade 3, grade 4, related, grade 3 related and grade 4 related events, if appropriate.

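### Safety, a primary endpoint, is grouped by assigned arm with no exception, so a misdosed patient's adverse events would count under a regimen not received

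*Combined protocol and SAP*

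**What the plan says.** Section 10.1 names as a primary endpoint: "Safety and Toxicity of the two regimens: adverse events and serious adverse events". Section 10.6.1 then sets one grouping rule for the whole analysis: "The patients will be analyzed according to the treatment group assigned by randomization". It is the first item under derived data, ahead of the immunogenicity and safety derivations, and carries no qualification.

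The other relevant sections are these:

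- 10.4.1, population: "The Total Treated Population will include all the enrolled patients that have received at least one dose of the study product".
- 10.4.2, approach: "The intent-to-treat approach will define the Total Treated Population to be used for data analysis of this trial".
- 10.6.3, adverse event derivation: "all patients treated will be considered. Patients who did not report an event will be considered as patients without the event".
- 10.7.5, safety population: "The safety analyses will be based on the Total Treated population".
- 10.7.5.1, adverse event percentages: "will be reported by treatment group with exact 95% confidence intervals".
- 10.3, toxicity: "Toxicity data will be summarized using the usual toxicity table by category and worst grade for the two ASCI regimens".

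Section 5.3.2 requires the treatment number actually used to be recorded in the CRF at each administration.

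**The concern.** Grouping by assigned arm is right for RFS, OS and the titre comparison, where the randomised contrast is the aim. For toxicity the question is what happens to patients exposed to Poly IC:LC, and assignment answers it only if every patient gets the assigned regimen. Poly IC:LC is a separate injection given 10 minutes after the ASCI (Section 5.2), over a schedule of 13 doses, so it can be left out or given in error.

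The grouping carries weight here because Section 8.7.2 tells investigators to judge causality against treatment administration as a whole when several treatments are given together, not against each product. Event-level attribution will therefore not isolate Poly IC:LC, and the comparison between arms has to do so. The arms are small, and Section 10.3 expects little toxicity and has no power calculation for safety, so single events can be visible in the tables.

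**Working it through.** **1. Does any section override 10.6.1 for safety?**

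- 10.4.1, 10.6.3 and 10.7.5 fix who is included (patients given at least one dose). They do not say in which arm a patient counts.
- 10.4.2 calls the approach intent-to-treat, which supports assigned-arm grouping.
- 10.7.5 to 10.7.5.2 report by treatment group, the term that 10.6.1 ties to randomisation.
- 10.3 refers to the two regimens without saying assigned or received, which is too loose to displace an explicit rule.

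No section gives an as-treated safety analysis or a rule for a patient who receives the wrong regimen.

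**2. Largest effect of one patient on one arm's rate.** Input: 20 patients per arm (Section 10.3). Suppose an assigned arm has x patients with the event out of 20, one of whom actually received the other regimen. Regrouping changes the rate from x/20 to (x − 1)/19:

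x/20 − (x − 1)/19 = (20 − x)/380

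This is largest at x = 1, where it is 19/380 = 1/20 = 5.0 points. In the arm that gains the patient, the rate goes from y/20 to (y + 1)/21, a change of (20 − y)/420. That is at most 20/420 = 4.8 points, at y = 0. If all 44 patients allowed are enrolled, 22 per arm, the first figure becomes 1/22 = 4.5 points.

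**3. Effect on the difference between arms.** The counts below are assumed, to show the mechanism; none is in the documents. In rows A to C the misdosed patients were assigned ASCI alone but received the combination, and each has the event. In row D one patient was assigned the combination but received ASCI alone, and has the only event.

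| Case | As assigned: combination vs ASCI alone | Difference | As received: combination vs ASCI alone | Difference |
|---|---|---|---|---|
| A: 1 misdosed, 2 other events on the combination | 2/20 vs 1/20 | +5.0 | 3/21 vs 0/19 | +14.3 |
| B: 2 misdosed, 2 other events on the combination | 2/20 vs 2/20 | 0.0 | 4/22 vs 0/18 | +18.2 |
| C: 1 misdosed, no other event | 0/20 vs 1/20 | −5.0 | 1/21 vs 0/19 | +4.8 |
| D: 1 misdosed, no other event | 1/20 vs 0/20 | +5.0 | 0/19 vs 1/21 | −4.8 |

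With no misdosed patient the two groupings are identical. Rows A and B show dilution; rows C and D show the sign reversing in either direction.

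**4. Scale against the planned precision.** The exact 95% interval for 1/20 runs from about 0.1% to 24.9%, and for 0/19 from 0% to 17.6%. A 5-point shift lies well inside that uncertainty.

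**5. Design figures.** The plan states no safety figure to reproduce. Its power for the titre comparison does reproduce: log10(10,500/7,000) = 0.1761; standard error 0.28 × √(2/20) = 0.0885; noncentrality 1.99; one-sided 0.05 with 38 degrees of freedom gives 62.1%, against 62% stated. Regrouping the safety data does not touch it.

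**The case against.** The trigger is hypothetical. The trial is open-label and at one centre, Poly IC:LC is a visible separate injection, and a web system returns a treatment number that is then recorded. Postponement and stopping (5.2.1.1, 5.2.1.2) are written for study treatment as a whole, so a combination patient who never receives Poly IC:LC would be a protocol deviation and not an expected pattern. The safety analysis is descriptive, with no hypothesis test. Serious events get narratives, related events are tabulated separately, and doses given and compliance are summarised, so a wrong regimen might well come to light. Grouping by assignment is also a prespecified choice that preserves the randomised comparison. All of this stands, and it keeps the point small. None of it regroups the patient in the main safety tables.

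A reader might infer that the rule hides an excess of toxicity on Poly IC:LC. The documents do not support that: no misdosing is reported, the table above rests on extreme assumed counts, and the direction of the error depends on which way the misdosing goes.

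A reader might also infer that the Total Treated label already means analysis as treated. It settles inclusion only.

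A simple split of any Poly IC:LC against none is tempting as a remedy, but it would misattribute events too. A control patient given Poly IC:LC in error only at dose 13 would have every event after doses 1 to 12 moved to the combination group.

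**Conclusion.** The point holds as a conditional, minor weakness. The plan applies assigned-arm grouping to a primary safety endpoint without exception, and for any patient given the other regimen this books events to a regimen not received. The size is up to 5 points in one arm's rate per such patient with 20 per arm, and nil if every patient receives the assigned regimen. The documents give no misdosing rate, so no expected effect can be stated; it is probably small. The conclusion rests on reading treatment group in 10.7.5 as 10.6.1 defines it, which is the only definition the plan offers. Prespecifying the rule also avoids choosing a grouping after open-label events are known.

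**What to change.** Add to 10.6.1 or 10.7.5:

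- Safety is tabulated by regimen actually received.
- A patient with mixed exposure is grouped by the regimen received for the majority of doses and is also listed separately, with each event shown against whether Poly IC:LC had been given before onset. The text should say where an exact tie is placed.
- RFS, OS and the titre comparison remain by assigned arm.

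The cost is a short addition to the analysis plan and a little programming. The treatment number is already recorded at each administration, but the glossary defines it as identifying a treatment, which may be a set of products. The sponsor should therefore confirm that the CRF shows whether Poly IC:LC itself was given. The downside is that the safety tables no longer strictly follow randomisation if any patient is misdosed. Sample size, significance level and power are unchanged.

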10.6.2. Immunogenicity

The cut-off value of the ELISA assay is defined by the laboratory before the analysis and is described in Section 6.4.6.

- A seropositive patient is a patient whose titre is greater than or equal to the cut-off value. The seropositivity rate is defined as the proportion of seropositive patients.
- Antibody response is defined as antibody concentrations \geq the cut-off value among patients with concentrations $<$ the cut-off value before treatment initiation and as antibody concentration at least twice the patient's own baseline value among patients with concentrations \geq the cut-off value before treatment initiation.
- The Geometric Mean Titre (GMT) is calculated by taking the anti-logarithm of the mean of the log concentration transformations. Antibody titres below the cut-off value of the assay will be given an arbitrary value of half the cut-off value for the purpose of this calculation.
- For a given patient and a given immunogenicity measurement, results of missing or non-evaluable measurements will not be replaced. Therefore, an analysis will exclude patients with missing or non-evaluable measurements.

10.6.3. Safety

For the analysis of adverse events, such as serious adverse events or adverse events by primary MedDRA term, all patients treated will be considered. Patients who did not report an event will be considered as patients without the event.

10.7. Final analyses

All statistical analyses will be performed using SAS, R and/or StatXact statistical software.

10.7.1. Analysis of demographics and other baseline characteristics

Demographic characteristics (age, gender, etc.) and other baseline characteristics such as MAGE-A3 expression of the tumor specimen, tumor classification, previous surgery etc. for all patients randomized will be tabulated and analyzed by appropriate descriptive statistics:

- Frequency tables will be generated for categorical variables such as gender;
- Mean, median, SD, range, and interquartiles will be provided for continuous data such as age. These data will be tabulated by treatment group, and the tables will be repeated for the different analysis populations: Total Treated Population, ATP cohort for \clinical activity and ATP cohort for immunogenicity.

10.7.2. Analysis of treatment compliance and treatment modifications

The total number of doses administered and the length of follow-up will be summarized.

For the Total Treated population cohort, overall compliance will be calculated for each dose as the percentage of patients who received the dose as per protocol (see Section 10.4) among all patients still on treatment at the target day of dose administration. Compliance will be considered unknown if it cannot be calculated because of missing data. Dose delays recorded on the CRF will not be taken into account in the measure of compliance.

The number of patients discontinuing treatment with the investigational product, as well as the reason for discontinuation, will be summarized and listed.

These data will be tabulated by treatment group for the total treated population.

10.7.3. Analysis of clinical activity

10.7.3.1. Relapse-free survival (RFS)

10.7.3.1.1. Relapse-free survival in the overall study population (secondary objective)

The analysis of RFS will be performed on the overall study Total Treated population. The primary analysis will be based on the adjusted Cox regression model.

Estimates of HR and their 95% CI will be obtained and the Wald test will be used to compare the groups.

Events of relapse of disease will be assigned to the visit at which they are detected (see Relapse Algorithm in Section 6.3.12), ignoring previously missed evaluation visits.

Or rather, interval-censored time-to-event data analysis methods such as Turnbull's (1976) and Finkelstein's (1985) could be used.)

This primary analysis will be complemented by the following sensitivity analyses:

- an analysis of RFS based on the adjusted Cox regression model (see above) performed on the Total treated population, taking the date of first missed evaluation visit before detection of recurrence as date of event for patients not compliant with the scheduled evaluations;

- an unadjusted analysis of RFS based on the Logrank test, performed on the Total treated population. For the purpose of this sensitivity analysis, estimates of HR and their 95% CIs will be obtained by an unadjusted Cox model. More details will be given in the Report Analysis Plan (RAP).

10.7.3.2. Overall survival (Secondary objective)

The analysis of Overall survival will include the analysis of Overall survival in the overall study population, the analysis of Overall survival in the population of patients presenting the potentially favorable gene signature and the analysis of Overall survival in the population not presenting this gene signature. These analyses will be performed using the same methods as those described for the primary analysis of RFS (see Section 10.7.3.1.1).

10.7.4. Analysis of immunogenicity

The analysis of immunogenicity will be performed on the ATP population, cf. Section 10.4.3.

The immunogenicity induced by the recMAGE-A3 + AS15 +/- poly IC:LC ASCI will be assessed through calculation of the geometric mean titres (with 95% CI), the proportion of seropositive patients and antibody response in the two treatment groups. This will be done for antibodies at baseline, after 2, 4, 6, 7, and 9 dose administrations and post-treatment (i.e., at the concluding examination at Visit 14, 3 months after the injection of dose 13, cf. Section 6.3).

Antibody titres may also be investigated using reverse cumulative curves.

A possible correlation between the immunological response (such as antibody response to MAGE-A3) and RFS may be explored using a time-dependent Cox model.

The immunogenicity will also be evaluated in the gene signature-positive and gene signature negative populations, separately.

10.7.5. Analysis of safety

The safety analyses will be based on the Total Treated population.

The duration of treatment and total number of doses of investigational product administered will be summarized by treatment group.

10.7.5.1. Adverse events

Adverse events (AEs), including abnormal laboratory values, will be graded according to the CTCAE, Version 4.0 and coded to the preferred term (PT) level using the MedDRA dictionary.

The percentage of patients with adverse event(s) within 30 days of each recMAGE-A3 + AS15 ASCI dose +/- Poly IC:LC will be reported by treatment group with exact 95% confidence intervals, as per MedDRA terminology, by Preferred Term (PT) and System Organ Class (SOC), if appropriate. The same tabulation will be presented for grade 3, grade 4, related, grade 3 related and grade 4 related events, if appropriate.

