8.6. Time period, frequency, and method of detecting adverse and serious adverse events

All AEs occurring within 30 days following administration of each dose of the study treatment must be recorded on the Adverse Event form in the patient's CRF, irrespective of intensity or whether or not they are considered to be related to the treatment administration.

The standard time period for collecting and recording SAEs (except autoimmune SAEs see below) will begin at randomization or the first receipt of study treatment and will end at the concluding visit (Visit 14, Month 30) or until 30 days after the administration of the last dose of study treatment in the event of early discontinuation of study treatment administration. See Section 8.9 for instructions on reporting and recording SAEs.

Onsets of potential immune mediated diseases (pIMD) or autoimmune disease occurring throughout the study (from Visit 1 until the end of the follow-up period) must be recorded as AE or SAE, as appropriate, in the patient CRF (see Section 8.3). Appropriate documentation of the diagnosis of autoimmune diseases must be provided in each instance.

An overview of the protocol-required reporting periods for adverse events and serious adverse events is given in Table 9.

Study activity	Screening phase	Treatment phase				Concluding visit	Follow-up
	From ICF signature to Visit 1	Visit 1	30 days post Visit 1	Visit X (X=2 to 13)	30 days post Visit X	Visit 14	Till 5 years after first administration or study withdrawal
Reporting of AEs ^a							
Reporting of SAEs ^a							
Reporting of autoimmune diseases							
Reporting of SAEs related to study participation and concurrent GSK medications ^b							

CONFIDENTIAL

- i. Except autoimmune AEs and SAEs which are reported till end of follow-up.
- j. Surgical resection of the tumor and adjuvant chemotherapy administration are not considered as study procedures; SAEs related to these treatments should not be recorded.

Table 10. Reporting periods for adverse events and serious adverse events

The investigator will inquire about the occurrence of AEs/SAEs and pIMD at every visit/contact during the study and throughout the follow-up period.

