10.3. Study design/sample size and power/data analyses

Study Design

This is a 1:1 randomized, two-arm, open-label, Phase II, single-center study to evaluate the safety, tolerability and immunogenicity of recMAGE-A3 + AS15 ASCI with Poly IC:LC as adjuvant therapy compared to recMAGE-A3 + AS15 ASCI alone in MAGE-A3 positive patients with completely resected stage IV melanoma. Secondary objectives include: to describe the efficacy in terms of Relapse-Free Survival (RFS) and Overall Survival (OS) of the two arms; to collect preliminary data on the T cell immune response to the ASCI in the overall study population as well as subsets of patients of interest (e.g., arms and gene signature groups), and to evaluate the gene signature in all patients when possible. The study treatment will consist of an induction phase and a maintenance phase. During the induction phase, immunization with or

without Poly IC:LC will be administered 5 times at 3-week intervals. During the maintenance phase, immunization with recMAGE-A3 + AS15 with or without Poly IC:LC will be administered 8 times at 3-month intervals. The 13 immunizations with or without Poly IC:LC will be administered over a period of 27 months. The total duration of the study treatment phase (including concluding visit) is 30 months per patient. The duration of active follow-up for survival, recurrence and serious adverse events (SAEs) related to the study participation and concurrent GSK medications will be 5 years from the first administration of study treatment.

Sample Size/Power Calculations and Accrual

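### Adverse events are compared as crude patient percentages, so if one arm stays on treatment longer, equal per-dose toxicity will on average look somewhat higher in that arm

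*Combined protocol and SAP*

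**What the plan says.** Safety and tolerability, compared between arms, is one of two primary objectives (Section 2.1). The relevant text is:

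- **Collection** (Section 8.6): "All AEs occurring within 30 days following administration of each dose of the study treatment must be recorded".
- **Planned exposure** (Section 10.3): "The 13 immunizations with or without Poly IC:LC will be administered over a period of 27 months". Section 5.2.1.2 ends dosing at relapse or at treatment-related grade 3 or 4 toxicity, among other reasons.
- **Summaries**: Section 10.7.5.1 gives "The percentage of patients with adverse event(s) within 30 days of each recMAGE-A3 + AS15 ASCI dose", by arm, with exact 95% intervals. Section 10.3 says "Toxicity data will be summarized using the usual toxicity table by category and worst grade for the two ASCI regimens".
- **Denominator** (Section 10.6.3): "all patients treated will be considered", and "Patients who did not report an event will be considered as patients without the event".
- **Exposure summary** (Section 10.7.5): "The duration of treatment and total number of doses of investigational product administered will be summarized by treatment group". Section 10.7.2 adds discontinuations with reasons, and compliance at each dose among patients still being treated when that dose was due.
- **Expected RFS** (Section 10.3): a median of 12 months on ASCI alone, with a possible doubling to 24 months when Poly IC:LC is added.

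No adverse-event rate per dose or per unit of time, and no time-to-event summary of adverse events, is planned.

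**The concern.** The number of doses a patient receives is decided after randomization, largely by relapse. Each further dose opens another 30-day window in which an event can be recorded. A percentage of patients with any event, or a worst grade over all doses, therefore mixes toxicity per dose with time on treatment. If Poly IC:LC prolongs RFS as the plan hopes, its arm has more opportunity to record events even when each injection is no more toxic. If the combination were instead stopped earlier, the crude tables could understate its toxicity. That reverse effect is only partial, because a patient who stops for toxicity has already been counted with that event. The question at stake is whether adding Poly IC:LC makes the injections harder to tolerate.

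**Working it through.** **1. The plan's own figure.** No figure is given for adverse events. The RFS medians can be checked through the stated RFS power of about 61%. Take exponential RFS, 36 months of follow-up after accrual, and accrual over 44/2.5 = 17.6 months. With λ = ln 2/median, F = 36 and A = 17.6, the probability of an event is 1 − [e^(−λF) − e^(−λ(F+A))]/(λA), which is 0.92 and 0.72 in the two arms. Expected events are 20 × (0.9215 + 0.7228) = 32.9. Freedman's formula at a hazard ratio of 0.5 and one-sided 0.05 gives Φ(√32.9/3 − 1.645) = Φ(0.267) = 0.605. The stated power is reproduced, so exponential RFS with medians of 12 and 24 months is a fair rendering of the plan's expectation.

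**2. Inputs.** From the documents: doses at weeks 0, 3, 6, 9 and 12, then at months 6 to 27 every 3 months (Tables 5 and 6); medians of 12 and 24 months. Assumed: relapse is the only reason to stop, and the per-dose event probability p is constant, independent between doses and equal in both arms. The documents give no value for p, so a range is shown.

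**3. Exposure.** The probability of reaching dose k at time t_k is S(t_k) = 0.5^(t_k/median), in calendar months.

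| | Dose 5 | Dose 6 | Dose 8 | Dose 10 | Dose 13 | Mean doses = Σ S(t_k) |
|---|---|---|---|---|---|---|
| Median 12 | 0.853 | 0.707 | 0.500 | 0.354 | 0.210 | 7.96 |
| Median 24 | 0.923 | 0.841 | 0.707 | 0.595 | 0.459 | 9.87 |

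The ratio of mean doses is 9.87/7.96 = 1.24.

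**4. Crude percentage with equal per-dose risk.** P(any event) = Σ_k S(t_k) × p × (1 − p)^(k−1), over k = 1 to 13.

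| p | Median 12 | Median 24 | Excess (points) |
|---|---|---|---|
| 0.01 | 7.6% | 9.4% | 1.8 |
| 0.02 | 14.6% | 17.9% | 3.2 |
| 0.05 | 32.4% | 38.7% | 6.3 |
| 0.10 | 53.5% | 61.8% | 8.3 |
| 0.20 | 76.8% | 84.1% | 7.3 |
| 0.50 | 95.7% | 97.7% | 2.0 |

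(Excesses are computed before rounding.)

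**5. The two alternatives.** Over 20,000 simulated trials at p = 0.10, events per dose administered are 0.100 in both arms. For induction alone at p = 0.10, the sum over the first five doses is 0.1 × (1 + 0.9×0.961 + 0.81×0.923 + 0.729×0.887 + 0.656×0.853) = 38.2% on ASCI alone. The same sum is 39.5% on the combination.

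**6. Sensitivity.** With medians of 12 and 18 months, the excess at p = 0.10 is 5.2 points; with equal medians it is zero. Using Table 6's week column for maintenance doses gives mean doses of 8.2 and 10.0, and about 54% against 63% at p = 0.10. In simulated trials of 20 per arm with p from 0.02 to 0.20, the longer-treated arm shows the higher crude percentage in 52% to 65% of trials and the lower in 21% to 31%.

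**The case against.** The best defence is that crude incidence and worst-grade tables answer a legitimate question: how many patients given this regimen had the event over its actual course. They are descriptive, with intervals and no planned between-arm test, in a trial powered only for the immune endpoint. Doses, duration and reasons for stopping are tabulated by arm, so a reader can see unequal exposure. The largest excess, 8.3 points, is 0.083 × 20 = 1.7 patients, while the exact 95% interval for 8 of 20 runs from 19% to 64%. All of this stands. It limits the size of the point, but no planned table separates toxicity per dose from exposure, and a total dose count cannot be matched to individual event terms.

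A reader might infer three stronger things that the documents do not support.

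- *That the tables will show a false toxicity difference.* The shift holds on average; in a sizeable minority of simulated trials it goes the other way. The plan also says only that Poly IC:LC might double RFS.
- *That tables by dose number would count patients who never received a dose as having tolerated it.* With all treated patients as denominator, a true 20% risk at dose 13 would appear as 0.20 × 0.210 = 4.2% against 0.20 × 0.459 = 9.2%. But that table arises only by joining the general rule of Section 10.6.3 to the wording of Section 10.7.5.1. The text can equally mean recipients of the dose, and then this dilution vanishes. Section 10.7.2 uses an on-treatment denominator for compliance. The denominator is unspecified, not shown to be wrong.
- *That earlier stopping for toxicity would hide that toxicity.* The event that led to stopping is already counted; only later or different events are missed.

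**Conclusion.** The point holds as a modest improvement to the safety analysis. If time on treatment differs between arms, equal recurring per-dose toxicity gives a higher expected crude percentage in the longer-treated arm. Under the plan's RFS expectation the excess is about 2 to 8 points for per-dose risks of 1% to 20%. It fades for very common events, and is nil for events confined to the first dose or when exposure is equal. These sizes rest on exponential RFS, relapse as the only reason to stop, and assumed constant per-dose risks that the documents do not supply. The crude tables are a valid summary, but alone they are a weak basis for comparing tolerability between arms.

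**What to change.** Keep the crude and worst-grade tables. In Section 10.7.5.1 add:

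1. Adverse events per dose administered, by arm, overall and for the main categories, with intervals that allow for repeated events within a patient (for example, a bootstrap that resamples patients).
2. A separate table for induction (doses 1 to 5), where exposure is nearly equal.
3. If tables by dose number are produced, a statement that the denominator is the patients who received that dose, in line with the approach of Section 10.7.2.

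The first two belong together. A per-dose rate assumes roughly constant risk: an event confined to the first dose with 20% risk would give 0.20/7.96 = 2.5 against 0.20/9.87 = 2.0 events per 100 doses, an artefact in the other direction. The crude and induction tables guard against that.

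Doses and adverse events are already recorded. The cost is a few columns and slightly longer safety tables, with no change to treatment or data collection.
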